4.2.1 Inclusion Criteria

1) Signed Written Informed Consent

- a) Before any study procedures are performed, subjects will have the details of the study described to them, and they will be given a written informed consent document to read. Then, if subjects consent to participate in the study, they will indicate that consent by signing and dating the informed consent document in the presence of study personnel.

2) Target Population

- a) Subjects with a diagnosis of Impaired Glucose Tolerance or Prediabetes i.e. fasting plasma glucose between 100-125 mg/dl, or 2 hour post 75 gram OGTT plasma glucose between 140-199 mg/dl, or HbA1c 5.7-6.4% as per revised ADA criteria (24)
- b) **Age and Reproductive Status**
- c) Men and women, ages 30 to 70 years.
 - i) Women of childbearing potential (WOCBP) must be using an acceptable method of contraception to avoid pregnancy throughout the study in such a manner that the risk of pregnancy is minimized.
 - ii) Women must have a negative serum or urine pregnancy test (minimum sensitivity 25 IU/L or equivalent units of HCG) within 72 hours prior to the start of investigational product.

iii) Women must not be breastfeeding.

Women of childbearing potential include any female who has experienced menarche and who has not undergone successful surgical sterilization (hysterectomy, bilateral tubal ligation, or bilateral oophorectomy) or is not postmenopausal. Post menopause is defined as:

- Amenorrhea ≥ 12 consecutive months without another cause and a documented serum follicle stimulating hormone (FSH) level > 35 mIU/mL, or
- Women with irregular menstrual periods and a documented serum follicle stimulating hormone (FSH) level > 35 mIU/mL, or

NOTE: FSH level testing is not required for women ≥ 62 years old with amenorrhea of ≥ 1 year.

- Women on hormone replacement therapy (HRT).

Women who are using oral contraceptives, other hormonal contraceptives (vaginal products, skin patches, or implanted or injectable products), or mechanical products such as an intrauterine device or barrier methods (diaphragm, condoms, spermicides) to prevent pregnancy, or are practicing abstinence or where their partner is sterile (eg, vasectomy) should be considered to be of childbearing potential.

- d) Patients must have been on a stable dose of allowed chronic medications such as statins and other lipid lowering therapy for 90 days prior to entering the study.
- e) Patients must have a BMI between 30-35 kg/m². Only subjects whose body weight has been stable ($\pm 3-4$ pounds) over the three months prior to study will be included.
- f) Patients must have the following laboratory values:
 - Hematocrit ≥ 34 vol%
 - S. creatinine < 1.5 mg/dl in men and 1.4 mg/dl in women
 - AST (SGOT) < 2.5 times upper limit of normal
 - ALT (SGPT) < 2.5 times upper limit of normal
 - Alkaline phosphatase < 2.5 times upper limit of normal

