Saxagliptin may be administered without regard to meals. No dosage adjustment is considered necessary in elderly subjects on the basis of age. Body mass index (BMI), T2DM, gender, age, race, hepatic impairment, and mild renal insufficiency had no clinically meaningful effects on the pharmacokinetics of saxagliptin or BMS-510849. In subjects with moderate to severe renal impairment, and end stage renal disease (i.e., creatinine clearance <50 mL/min), area under curve (AUC) values for saxagliptin and/or BMS-510849 were generally greater than 2-fold higher than the AUC values in healthy subjects.

Co-administration of saxagliptin with the following drugs had no meaningful effect on the pharmacokinetics of saxagliptin, BMS-510849, or the other drug tested: metformin, glyburide, pioglitazone, digoxin, or simvastatin. Co-administration of saxagliptin and ketoconazole or diltiazem dosed to steady-state resulted in up to 1.6- and 2.5-times increase in saxagliptin maximum observed concentration (C_{max}) and area under curve extrapolated to infinity [AUC(INF)] values, respectively, and up to an 8-times decrease in the exposure to BMS-510849. However, the systemic exposures to the total active moieties of saxagliptin (saxagliptin + BMS-510849 corrected for relative differences in potency of DPP-IV inhibition) were not meaningfully altered by diltiazem or ketoconazole. Co-administration of saxagliptin with gastric acid controllers: aluminum and magnesium hydroxides + simethicone, famotidine or omeprazole did not meaningfully alter the pharmacokinetics of saxagliptin or BMS-510849.

More detailed information on clinical pharmacokinetics of saxagliptin may be found in the Investigator Brochure (Sections 5.1 and 5.2) (3).

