1.1.3 Summary of Safety Results in Subjects with Type 2 Diabetes Mellitus

Once-daily, orally administered saxagliptin was safe and well-tolerated at doses of up to 400 mg QD for 2 weeks, 100 mg QD for 6 weeks, 40 mg QD for 12 weeks, and at doses of 2.5, 5, and 10 mg QD for up to 102 weeks. In an extensive Phase 2b/3 program, the majority of reported adverse events (AEs) was of mild intensity and did not require treatment discontinuation. The safety profile was generally consistent with placebo or comparator when saxagliptin was given as monotherapy, as add-on combination treatment to metformin, SU, or TZD, and as initial therapy in combination with metformin. Although the rate of certain AEs was higher in subjects who received

saxagliptin 10 mg compared with those who received 2.5 and 5 mg, saxagliptin 10 mg was also safe and well tolerated, providing a safety margin for the saxagliptin 5 mg dose.

The placebo-controlled pooled safety analysis, which included the two monotherapy studies (CV181011 and CV181038), and the add on combination studies (CV181014, CV181013, CV181040 with metformin, TZD, glyburide, respectively), demonstrated that the overall incidence of AEs in subjects treated with saxagliptin 5 mg was similar to placebo (72.2% vs. 70.6%). The majority of reported AEs was of mild intensity and did not require treatment discontinuation. There was no discernible difference in the clinical AE profile between the saxagliptin 2.5 mg and 5 mg doses. The most frequently reported AEs (incidence $\geq 5\%$) in active vs. placebo group were upper respiratory tract infection (7.7% vs. 7.6%), headache (7.0% vs. 5.9%), nasopharyngitis (6.0% vs. 6.8%), urinary tract infection (5.8% vs. 6.1%), diarrhea (5.2% vs. 6.1%), and back pain (3.9% vs. 5.1%). In the combination study with metformin (CV181-039) headache (7.9% in saxagliptin, 5.2% in metformin) and diarrhea (6.4% in saxagliptin, 7.3% in metformin) were the most frequently reported AEs (incidence $\geq 5\%$).

In the placebo-controlled pooled safety analysis the frequency of serious adverse events (SAEs) was identical (3.4%) for the saxagliptin 5 mg and placebo groups. The frequencies of SAEs were comparable for the saxagliptin 5 mg plus metformin and metformin monotherapy groups (2.5% and 2.4%, respectively) in the combination with metformin study (CV181039).

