4 INVESTIGATIONAL PLAN

4.1 Study Design and Duration

Subjects:

40 obese subjects with impaired glucose tolerance (IGT) or prediabetes, (fasting plasma glucose between 100-125 mg/dl, or 2 hour post 75 gram OGTT plasma glucose between 140-199 mg/dl, or HbA1c 5.7-6.4%) who are free of other major organ system disease will be studied. Subjects will range in age from 30 to 70 years and in body mass index from 30-35 kg/m². Subjects who have previously received or are taking metformin, DPP-IV inhibitors, exenatide, liraglutide, or a thiazolidinedione for treatment of IGT will be excluded. Patients on statins and other lipid lowering therapy will be included provided they are on a stable dose of lipid lowering therapy for at least 3 months prior to enrollment. The dose of the lipid lowering therapy will not be changed for the entire duration of the study. The fasting plasma glucose must be ≤ 125 mg/dl, 2 hour post 75 gram OGTT plasma glucose must be less

than 200 mg/dl, and HbA1C must be < 6.5% to be included in the study. Subjects with clinically significant cardiac, hepatic, or renal disease will not be studied. Subjects will be recruited from the Endocrine/Diabetes/Obesity Clinic at the Baylor Clinic. All subjects will be recruited by direct contact from [name] or one of the co-investigators.

Study Design: All subjects will participate in an initial screening visit (medical history and physical exam, urinalysis, EKG, CBC, liver function tests (LFTs), serum creatinine, lipid profile, HbA1c; and a fasting and 2 hour plasma glucose (during a 75 gram OGTT). During the 2 hour OGTT (75 grams), glucose, insulin, c-peptide, and FFA determinations will be made at baseline (fasting) and every 15-30 minutes and insulin sensitivity will be calculated by the Matsuda Index. In addition, plasma triglycerides will be measured at baseline and at 120 minutes during the OGTT.

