5.4 Selection and Timing of Dose for Each Subject

The recommended dose of saxagliptin is 5 mg once daily. Saxagliptin can be taken with or without food. We shall administer saxagliptin 5 mg once daily PO for 6 months.

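### The only numeric renal entry limit, a fixed serum creatinine in 4.2.1(f), can admit patients with estimated clearance below the 50 mL/min boundary in Section 1.1.1

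*Combined protocol and SAP*

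**What the plan says.** The quantified renal criterion is in Section 4.2.1, item 2(f): "S. creatinine < 1.5 mg/dl in men and 1.4 mg/dl in women". I read the less-than sign as applying to both sexes. Section 4.2.2 contains no renal exclusion and no clearance limit. Age may be up to 70, and item 2(e) fixes body mass index: "Patients must have a BMI between 30-35" kg/m².

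Section 4.1 adds two unquantified safeguards. Subjects are those "who are free of other major organ system disease will be studied", and "Subjects with clinically significant cardiac, hepatic, or renal disease will not be studied".

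Section 1.1.1 describes renal function on a different scale. It reports no clinically meaningful pharmacokinetic effect of mild renal insufficiency. It then turns to a worse-function group, "In subjects with moderate to severe renal impairment, and end stage renal disease", which it defines by "creatinine clearance <50 mL/min), area under curve (AUC) values for saxagliptin and/or BMS-510849 were generally greater than 2-fold higher" than in healthy subjects.

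The dose is the same for everyone on active drug (Section 5.4): "We shall administer saxagliptin 5 mg once daily PO for 6 months". The Section 6.1 schedule measures creatinine at screening and again at weeks 14 and 26.

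**The concern.** A fixed creatinine value corresponds to very different clearances depending on age, sex and body size. The entry limit varies only by sex, while the protocol's own pharmacokinetic boundary is a clearance. The two need not agree, and nothing in the plan links them.

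An investigator who recognises a clearance below 50 mL/min can exclude the patient under Section 4.1. But a patient whose creatinine passes 4.2.1(f) gives no automatic prompt to look further, because no clearance calculation is required. At stake is avoidable extra drug exposure for some patients on saxagliptin, in a prediabetic population, whereas the safety record that the protocol summarises comes from type 2 diabetes. This is a question of participant safety and clear eligibility rules, not of the efficacy analysis.

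**Working it through.** The plan states no clearance figure for its creatinine limits, so there is nothing to reproduce. The check converts the limits to clearance.

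**Inputs from the protocol.** Creatinine limits (4.2.1, 2(f)), taken at the highest passing two-decimal values, 1.39 mg/dl for women and 1.49 for men; age up to 70; BMI 30 to 35; boundary 50 mL/min (1.1.1).

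**Assumptions.** The protocol gives no clearance equation, weight basis or heights. I use Cockcroft-Gault and a range of heights.

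- Clearance = (140 − age) × weight / (72 × creatinine), times 0.85 in women.
- Actual weight = BMI × height².

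**Women aged 70 at 1.39 mg/dl, actual weight.** The denominator is 72 × 1.39 = 100.08. At 160 cm and BMI 30, weight is 76.8 kg, so clearance = 70 × 76.8 × 0.85 / 100.08 = 45.7 mL/min. Likewise:

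| BMI | 150 cm | 155 cm | 160 cm | 165 cm |
|---|---|---|---|---|
| 30 | 40.1 | 42.9 | 45.7 | 48.6 |
| 32.5 | 43.5 | 46.4 | 49.5 | 52.6 |
| 35 | 46.8 | 50.0 | 53.3 | 56.7 |

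**Height below which a woman at 1.39 mg/dl is under 50 mL/min, actual weight.** Weight at clearance 50 = 50 × 72 × 1.39 / (0.85 × (140 − age)), which is 84.1 kg at age 70, 73.6 kg at 60 and 65.4 kg at 50. Height = √(weight / BMI):

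| Age | BMI 30 | BMI 32.5 | BMI 35 |
|---|---|---|---|
| 70 | 167 cm | 161 cm | 155 cm |
| 60 | 157 cm | 150 cm | 145 cm |
| 50 | 148 cm | 142 cm | 137 cm |

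For men aged 70 at 1.49 mg/dl, the weight at clearance 50 is 50 × 72 × 1.49 / 70 = 76.6 kg, or about 160, 154 and 148 cm at the three BMIs.

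**How close to the limit creatinine must be.** For a woman aged 70 at BMI 30, clearance reaches 50 at creatinine = 70 × weight × 0.85 / 3600, which is 1.12, 1.19, 1.27 and 1.35 mg/dl at 150, 155, 160 and 165 cm. Values between these and 1.4 pass entry with clearance below 50.

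**Sensitivity to the weight basis.** Ideal weight (kg) = 45.5 (women) or 50 (men) + 2.3 × (height in inches − 60). Adjusted weight = ideal + 0.4 × (actual − ideal). At BMI 30:

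| Patient | Actual | Adjusted | Ideal |
|---|---|---|---|
| Man aged 70, 165 cm, 1.49 mg/dl (weights 81.7 / 69.5 / 61.4 kg) | 53.3 | 45.4 | 40.1 |
| Woman aged 50, 155 cm, 1.39 mg/dl (weights 72.1 / 57.5 / 47.9 kg) | 55.1 | 44.0 | 36.6 |

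Both patients are above 50 mL/min on actual weight and below it on either alternative.

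**The case against.** The strongest reply is that the plan has no defect here. Section 1.1.1 summarises pharmacokinetics and sets no eligibility or dosing rule at 50 mL/min. Section 4.1 already allows such patients to be excluded, and Section 1.1.1's own label of moderate to severe impairment gives the investigator a reason to do so. Creatinine is rechecked on study, and Section 4.2.3 requires stopping for a laboratory abnormality that the investigator judges contrary to the subject's interest. Tolerability is reassuring: Section 1.1.3 says "saxagliptin 10 mg was also safe and well tolerated, providing a safety margin for the saxagliptin 5 mg dose", and reports higher doses given safely for shorter periods (40 mg daily for 12 weeks, 100 mg daily for 6 weeks). The trial plans 40 subjects, only some of them on active drug, so the number affected may be zero.

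Most of this stands, and it keeps the point small. It does not close the gap. The safeguards depend on someone recognising a low clearance that the plan never asks anyone to compute, and a stable creatinine just under the limit is not an obvious abnormality. The week 26 recheck comes when treatment stops.

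The same facts rule out stronger readings that a reader might infer:

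- That the plan breaks a renal dosing rule. It contains none.
- That patients at 40 to 49 mL/min will have doubled exposure. The reported increase pools moderate impairment through end-stage disease, so a doubling in that band is not shown.
- That patients with renal disease may enter freely. Section 4.1 excludes those whose disease is clinically significant.

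**Conclusion.** The point holds as a low-priority design improvement. The creatinine limit alone can admit patients with estimated clearance below 50 mL/min, and the plan has no numeric rule to catch them.

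On actual weight the group is narrow: mainly older, shorter women with creatinine near the limit, shrinking as BMI rises. The lowest figure in the table, 40.1 mL/min, needs age 70, 150 cm, BMI 30 and creatinine 1.39 together. A reader might infer from the actual-weight figures that men of 160 cm or taller, or women aged 50 of 150 cm or taller, cannot be affected. The documents do not support that, because they give no weight basis; on adjusted or ideal weight the group includes younger women and some men.

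The consequence is modest. Section 1.1.1 describes the pharmacokinetics as linear, so a doubling from 5 mg is roughly the exposure from 10 mg. Section 1.1.3 calls that dose safe and well tolerated, while noting more of certain adverse events; discontinuation for adverse events was 3.9% at 10 mg and 3.3% at 5 mg. Section 1.1.3.1 gives infection events of 40.1% and 35.9% respectively. No effect on a primary or secondary endpoint is claimed. The number affected is probably small and cannot be counted from the documents. The conclusion rests on Cockcroft-Gault and the assumed heights and weight bases.

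**What to change.** Keep the creatinine limits and add to 4.2.1, item 2(f): *and estimated creatinine clearance of at least 50 mL/min by Cockcroft-Gault using actual body weight, calculated from screening creatinine, age and sex*. Use the same 50 mL/min figure for the renal part of the Section 4.1 exclusion, so that the two sections agree.

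Actual weight is already needed for the BMI criterion. In the obese patients worked above it gives higher estimates than adjusted or ideal weight, so it excludes fewer people. Some patients who would be below 50 mL/min on another basis would therefore still enter; naming the basis at least makes the rule reproducible.

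The cost is one clause, one number in Section 4.1, and one calculation per patient from screening data. The downside is a few more screen failures, mainly among older women.

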4.2.2 Exclusion Criteria

1) Sex and Reproductive Status

a) WOCBP who are **unwilling or unable** to use an acceptable method to avoid pregnancy for the entire study period.

b) Women who are pregnant or breastfeeding.

2) Medical History and Concurrent Diseases

a) Type 1 or Type 2 diabetes mellitus (FPG > 125 mg/dl)

b) History of diabetic ketoacidosis or hyperosmolar nonketotic coma

3) Physical and Laboratory Test Findings

a) Patients with diabetic gastroparesis will be excluded.

b) Patients with a history of clinically significant heart disease (New York Heart Classification greater than class 2; more than non-specific ST-T wave changes on the EKG), peripheral vascular disease (history of claudication), or pulmonary disease (dyspnea on exertion of one flight or less; abnormal breath sounds on auscultation) will not be studied.

4) Allergies and Adverse Drug Reactions

a) Subjects with a history of any serious hypersensitivity reaction to saxagliptin or DPP-IV inhibitor.

5) Prohibited Treatments and/or Therapies

a) Treatment with strong systemic cytochrome P450 3A4/5 (CYP 3A4/5) inhibitors.

b) Patients must not be on or have received any antihyperglycemic treatment for treatment of IGT at any time. Patients must not be receiving any of the following medications: thiazide or furosemide diuretics, beta-blockers, or other chronic medications such as hormone replacement therapy with known adverse effects on glucose tolerance levels. Patients must not be on systemic glucocorticoids.

6) Other Exclusion Criteria

a) Prisoners, or subjects who are involuntarily incarcerated.

b) Subjects who are compulsorily detained for treatment of either a psychiatric or physical (eg, infectious disease) illness.

Eligibility criteria for this study have been carefully considered to ensure the safety of the study subjects and to ensure that the results of the study can be used. It is imperative that subjects fully meet all eligibility criteria.

4.2.3 Discontinuation of Subjects from Treatment

Subjects MUST discontinue investigational product (and noninvestigational product at the discretion of the investigator) for any of the following reasons:

- Withdrawal of informed consent (subject's decision to withdraw for any reason).
- Any clinical adverse event (AE), laboratory abnormality, or intercurrent illness which, in the opinion of the investigator, indicates that continued participation in the study is not in the best interest of the subject.
- Pregnancy
 - Instruct WOCBP to contact the investigator or study staff immediately if they suspect they might be pregnant (eg, missed or late menstrual period) at any time during study participation. Institutional policy and local regulations should determine the frequency of on-study pregnancy tests for WOCBP enrolled in the study.
 - The investigator must immediately notify BMS if a study subject becomes pregnant. The mechanism for reporting pregnancy is described in Section 7.5.
- Termination of the study by BMS.
- Loss of ability to freely provide consent through imprisonment or involuntarily incarceration for treatment of either a psychiatric or physical (eg, infectious disease) illness
- Inability to comply with the protocol.

All subjects who discontinue should comply with protocol specified follow-up procedures as outlined in Section 6. The only exception to this requirement is when a subject withdraws consent for all study procedures or loses the ability to consent freely (ie, is imprisoned or involuntarily incarcerated for the treatment of either a psychiatric or physical illness). If a subject was withdrawn before completing the study, the reason for withdrawal must be entered on the appropriate case report form (CRF) page.

4.3 Data Safety Monitoring Plan

Protocol and consent form approval has been obtained from the Baylor College of Medicine IRB. Request for IND shall be submitted to the FDA. Prior to screening evaluations, each subject eligible for the study will be given an orientation session in which the nature and purpose of the study and the risks and benefits will be described. If an eligible subject agrees to participate in the study, he/she will be required to sign an informed consent form.

The PI and his team will monitor the study on a daily basis. All treatment emergent AEs will be recorded on source documents (i.e. original documents, data, and records). AEs include those reported spontaneously by the subject and those noted incidentally or as observed by the investigator or study personnel. All clinically significant abnormalities noted upon physical examination, or other diagnostic test results should be reported as an AE, except for baseline measurements that may be considered part of the medical history. In addition, all clinically significant AEs that continue at Study Termination will be followed up by the investigator and evaluated with additional tests if necessary, until the underlying cause is diagnosed or resolution occurs. All AEs will be evaluated for intensity and causal relationship with use of the study medication and/or study procedures by the investigator and reported to the Baylor IRB. All SAEs will be reported to the Baylor IRB and the sponsor within 24 hours. In addition, a safety report will be submitted to Baylor IRB annually. Any new information regarding saxagliptin will be submitted to Baylor IRB.

5 TREATMENTS

5.1 Study Treatment: Saxagliptin

An investigational product, also known as investigational medicinal product in some regions, is defined as follows: A pharmaceutical form of an active substance or placebo being tested or used as a reference in a clinical study, including products already with a marketing authorization but used or assembled (formulated or packaged) in a way different from the authorized form, or used for an unauthorized indication, or when used to gain further information about the authorized form. In this protocol, the investigational product is saxagliptin.

Other medications used as support or escape medication for preventative, diagnostic, or therapeutic reasons, as components of the standard of care for a given diagnosis, may be considered as noninvestigational products. In this protocol, noninvestigational products are: *no noninvestigational products will be used in this study*

